## **9.6    Concomitant Medications**

The summary table for all concomitant medications reported during the study will be made by standardized name in each medication class, using descriptive statistics (count and percentage).

# **10.       ANALYSIS OF EXPLORATORY ENDPOINTS**

## **10.1    Immunogenicity Assessment**

The incidence of TEADA (including preexisting ADA) to LY3451838 will be summarized in three categories: Subject evaluable for TEADA, Subject with ADA detected at baseline, and Subject with TEADA+ at postbaseline (Treatment-induced / Treatment boosted).

The summary will be performed by each cohort in LY3451838, overall LY3451838 and all placebo subjects combined.

Treatment-emergent ADAs are defined as those with a titer 2-fold (1dilution) greater than the minimum required dilution if no ADAs were detected at baseline (treatment-induced ADA) or those with a 4-fold (2 dilutions) increase in titer compared to baseline if ADAs were detected at baseline (treatment -boosted ADA). The minimum required dilution is 1:40.

## 10.2 Exploratory Assessment of PACAP Concentration

The results of PACAP concentration will be summarized using descriptive statistics at each of the scheduled visits, as well as the change from baseline. The summary will be performed by each cohort in LY3451838, overall LY3451838 and all placebo subjects combined.

## 11. ANALYSIS OF PK ENDPOINTS

The PK analysis are not in the scope of this SAP and are planned to be documented and performed by a third party.

## 12. LIST OF TABLES AND DATA LISTINGS

### 12.1 Statistical Tables

The statistical tables are to be generated using SAS version 9.4. In general, the sample size (n), minimum, and maximum are to be presented by whole number. The mean, standard deviation, and median are to be rounded and presented to one decimal place. For some values with meaningful decimal digits, their mean, standard deviation, and median will be rounded to more than one decimal place when necessary. The count will be the whole number. The percentage will be presented to one decimal place.

Disposition of Subjects and Baseline Characteristics:

Number	Title	Population
14.1.1	Disposition of Subjects	All
14.1.2	Demographics and Baseline Characteristics	Safety
14.1.3	Medical History	Safety

## Safety – Adverse Events

Number	Title	Population
14.3.1.1	Number of Subjects with Treatment-Emergent Adverse Events	Safety
14.3.1.2	Number of Treatment-Emergent Adverse Events	Safety
14.3.1.3	Number of Subjects with TEAE by MedDRA System Organ Class / Preferred Term	Safety
14.3.1.4	Number of Subjects with Serious TEAE by MedDRA System Organ Class / Preferred Term	Safety
14.3.1.5	Number of Subjects with TEAE by MedDRA System Organ Class / Preferred Term and Severity	Safety
14.3.1.6	Number of Subjects with TEAE by MedDRA System Organ Class / Preferred Term and Relationship to Study Drug	Safety
14.3.2.1	Listing of Serious TEAE	Safety

## Safety – Laboratory Test Results:

Number	Title	Population
14.3.4.1	Laboratory Test Results – Chemistry	Safety
14.3.4.2	Laboratory Test Results – Hematology	Safety
14.3.4.3	Laboratory Test Results – Urinalysis	Safety
14.3.4.4	Laboratory Test Results – C3, C4, CRP and ESR	Safety
14.3.4.5	Immunogenicity	Safety
14.3.4.6	PACAP Concentration	Safety

## Safety – Other:

Number	Title	Population
14.3.5.1	Vital Signs	Safety
14.3.5.2	Electrocardiogram (ECG)	Safety
14.3.5.3	Electrocardiogram (ECG) – Overall interpretation Shift from Baseline	Safety
14.3.5.4	Neurological Examinations	Safety
14.3.5.5	Concomitant Medications	Safety

## 12.2 Data Listings

The following data listings would not be provided if the data listings of the raw data are already provided and suffice per sponsor's perspective. Data listings will be sorted by the subject ID and visits.

Number	Title
1	Subject Disposition
2	Demographics
3	Concomitant Medications
4	Medical History
5	Vital Signs
6	Physical Examination
7	Electrocardiogram (ECG)
8.1	Laboratory Test Results – Chemistry
8.2	Laboratory Test Results – Hematology
8.3	Laboratory Test Results – Urinalysis
8.4	Laboratory Test Results - C3, C4, CRP and ESR
9	Immunogenicity
10	PACAP Concentration
11	Adverse Events
12	Neurological Examinations

## 13. TABLE SHELLS

The following table shells are provided in order to provide a framework of the statistical analysis for the study. These shells may not be reflective of every aspect of the study, but are intended to show the general layout of the tables that will be included in the final report.

Eli Lilly and Company - PROTOCOL: J1H-MC-LAJA  
 A Safety, Tolerability, and Pharmacokinetics Study of LY3451838 in Healthy Subjects

Table 14.1.1 - Disposition of Subject

		LY3451838							Placebo	Overall
		Cohort 1 25mgIV	Cohort 2 75mgIV	Cohort 3 250mgIV	Cohort 4 500mgIV	Cohort 5 1000mgIV	Cohort 6 1500mgIV	Cohort 7 250mgSC		
Screened	xx									
Enrolled		xx	xx	xx	xx	xx	xx	xx	xx	xx
Treated	N	xx	xx	xx	xx	xx	xx	xx	xx	xx
	YES	x(xx.x%)	x(xx.x%)	x(xx.x%)	x(xx.x%)	x(xx.x%)	x(xx.x%)	x(xx.x%)	x(xx.x%)	x(xx.x%)
	NO	x(xx.x%)	x(xx.x%)	x(xx.x%)	x(xx.x%)	x(xx.x%)	x(xx.x%)	x(xx.x%)	x(xx.x%)	x(xx.x%)
Completed	N	xx	xx	xx	xx	xx	xx	xx	xx	xx
	YES	x(xx.x%)	x(xx.x%)	x(xx.x%)	x(xx.x%)	x(xx.x%)	x(xx.x%)	x(xx.x%)	x(xx.x%)	x(xx.x%)
	NO	x(xx.x%)	x(xx.x%)	x(xx.x%)	x(xx.x%)	x(xx.x%)	x(xx.x%)	x(xx.x%)	x(xx.x%)	x(xx.x%)

Program: 14.1.1.xxxx.sas

Eli Lilly and Company - PROTOCOL: J1H-MC-LAJA  
 A Safety, Tolerability, and Pharmacokinetics Study of LY3451838 in Healthy Subjects

Table 14.1.1 - Disposition of Subject (Safety)

Primary Reason for Discontinuation	LY3451838							Placebo	Overall
	Cohort 1 25mgIV	Cohort 2 75mgIV	Cohort 3 250mgIV	Cohort 4 500mgIV	Cohort 5 1000mgIV	Cohort 6 1500mgIV	Cohort 7 250mgSC		
N	XX	XX	XX	XX	XX	XX	XX	XX	XX
Adverse Event	x(xx.x%)	x(xx.x%)	x(xx.x%)	x(xx.x%)	x(xx.x%)	x(xx.x%)	x(xx.x%)	x(xx.x%)	x(xx.x%)
Death	x(xx.x%)	x(xx.x%)	x(xx.x%)	x(xx.x%)	x(xx.x%)	x(xx.x%)	x(xx.x%)	x(xx.x%)	x(xx.x%)
Entry Criteria Not Met	x(xx.x%)	x(xx.x%)	x(xx.x%)	x(xx.x%)	x(xx.x%)	x(xx.x%)	x(xx.x%)	x(xx.x%)	x(xx.x%)
Lost To Follow-Up	x(xx.x%)	x(xx.x%)	x(xx.x%)	x(xx.x%)	x(xx.x%)	x(xx.x%)	x(xx.x%)	x(xx.x%)	x(xx.x%)
Physician Decision	x(xx.x%)	x(xx.x%)	x(xx.x%)	x(xx.x%)	x(xx.x%)	x(xx.x%)	x(xx.x%)	x(xx.x%)	x(xx.x%)
Progressive Disease	x(xx.x%)	x(xx.x%)	x(xx.x%)	x(xx.x%)	x(xx.x%)	x(xx.x%)	x(xx.x%)	x(xx.x%)	x(xx.x%)
Protocol Violation	x(xx.x%)	x(xx.x%)	x(xx.x%)	x(xx.x%)	x(xx.x%)	x(xx.x%)	x(xx.x%)	x(xx.x%)	x(xx.x%)
Sponsor Decision	x(xx.x%)	x(xx.x%)	x(xx.x%)	x(xx.x%)	x(xx.x%)	x(xx.x%)	x(xx.x%)	x(xx.x%)	x(xx.x%)
Other	x(xx.x%)	x(xx.x%)	x(xx.x%)	x(xx.x%)	x(xx.x%)	x(xx.x%)	x(xx.x%)	x(xx.x%)	x(xx.x%)

Eli Lilly and Company - PROTOCOL: J1H-MC-LAJA  
 A Safety, Tolerability, and Pharmacokinetics Study of LY3451838 in Healthy Subjects

Table 14.1.2 Demographics and Baseline Characteristics (Safety)

		LY3451838								
		Cohort 1 25mgIV N=XX	Cohort 2 75mgIV N=XX	Cohort 3 250mgIV N=XX	Cohort 4 500mgIV N=XX	Cohort 5 1000mgIV N=XX	Cohort 6 1500mgIV N=XX	Cohort 7 250mgSC N=XX	Placebo N=XX	Overall N=XX
Age (years)	N	XX	XX	XX	XX	XX	XX	XX	XX	XX
	Mean	XX.X	XX.X	XX.X	XX.X	XX.X	XX.X	XX.X	XX.X	XX.X
	SD	XX.X	XX.X	XX.X	XX.X	XX.X	XX.X	XX.X	XX.X	XX.X
	Median	XX.X	XX.X	XX.X	XX.X	XX.X	XX.X	XX.X	XX.X	XX.X
	Minimum	XX	XX	XX	XX	XX	XX	XX	XX	XX
	Maximum	XX	XX	XX	XX	XX	XX	XX	XX	XX
Gender	N	XX	XX	XX	XX	XX	XX	XX	XX	XX
	Male	x(xx.x%)	x(xx.x%)	x(xx.x%)	x(xx.x%)	x(xx.x%)	x(xx.x%)	x(xx.x%)	x(xx.x%)	x(xx.x%)
	Female	x(xx.x%)	x(xx.x%)	x(xx.x%)	x(xx.x%)	x(xx.x%)	x(xx.x%)	x(xx.x%)	x(xx.x%)	x(xx.x%)
Race	N	XX	XX	XX	XX	XX	XX	XX	XX	XX
	AMERICAN INDIAN OR ALASKA NATIVE	x(xx.x%)	x(xx.x%)	x(xx.x%)	x(xx.x%)	x(xx.x%)	x(xx.x%)	x(xx.x%)	x(xx.x%)	x(xx.x%)
	ASIAN	x(xx.x%)	x(xx.x%)	x(xx.x%)	x(xx.x%)	x(xx.x%)	x(xx.x%)	x(xx.x%)	x(xx.x%)	x(xx.x%)
	BLACK OR AFRICAN AMERICAN	x(xx.x%)	x(xx.x%)	x(xx.x%)	x(xx.x%)	x(xx.x%)	x(xx.x%)	x(xx.x%)	x(xx.x%)	x(xx.x%)
	NATIVE HAWAIIAN OR OTHER	x(xx.x%)	x(xx.x%)	x(xx.x%)	x(xx.x%)	x(xx.x%)	x(xx.x%)	x(xx.x%)	x(xx.x%)	x(xx.x%)
	PACIFIC ISLANDER									
	WHITE	x(xx.x%)	x(xx.x%)	x(xx.x%)	x(xx.x%)	x(xx.x%)	x(xx.x%)	x(xx.x%)	x(xx.x%)	x(xx.x%)

Eli Lilly and Company - PROTOCOL: J1H-MC-LAJA  
 A Safety, Tolerability, and Pharmacokinetics Study of LY3451838 in Healthy Subjects

Table 14.1.2 Demographics and Baseline Characteristics (Safety)

		LY3451838							Placebo	Overall
		Cohort 1 25mgIV N=XX	Cohort 2 75mgIV N=XX	Cohort 3 250mgIV N=XX	Cohort 4 500mgIV N=XX	Cohort 5 1000mgIV N=XX	Cohort 6 1500mgIV N=XX	Cohort 7 250mgSC N=XX	Placebo N=XX	Overall N=XX
Ethnicity	N	XX	XX	XX	XX	XX	XX	XX	XX	XX
	HISPANIC OR LATINO	x(XX.X%)	x(XX.X%)	x(XX.X%)	x(XX.X%)	x(XX.X%)	x(XX.X%)	x(XX.X%)	x(XX.X%)	x(XX.X%)
	NOT HISPANIC OR LATINO	x(XX.X%)	x(XX.X%)	x(XX.X%)	x(XX.X%)	x(XX.X%)	x(XX.X%)	x(XX.X%)	x(XX.X%)	x(XX.X%)
Height (cm)	N	XX	XX	XX	XX	XX	XX	XX	XX	XX
	Mean	XX.X	XX.X	XX.X	XX.X	XX.X	XX.X	XX.X	XX.X	XX.X
	SD	XX.X	XX.X	XX.X	XX.X	XX.X	XX.X	XX.X	XX.X	XX.X
	Median	XX.X	XX.X	XX.X	XX.X	XX.X	XX.X	XX.X	XX.X	XX.X
	Minimum	XX	XX	XX	XX	XX	XX	XX	XX	XX
	Maximum	XX	XX	XX	XX	XX	XX	XX	XX	XX
Weight (kg)	N	XX	XX	XX	XX	XX	XX	XX	XX	XX
	Mean	XX.X	XX.X	XX.X	XX.X	XX.X	XX.X	XX.X	XX.X	XX.X
	SD	XX.X	XX.X	XX.X	XX.X	XX.X	XX.X	XX.X	XX.X	XX.X
	Median	XX.X	XX.X	XX.X	XX.X	XX.X	XX.X	XX.X	XX.X	XX.X
	Minimum	XX	XX	XX	XX	XX	XX	XX	XX	XX
	Maximum	XX	XX	XX	XX	XX	XX	XX	XX	XX

Program: 14.1.2.xxxx.sas

Eli Lilly and Company - PROTOCOL: J1H-MC-LAJA  
 A Safety, Tolerability, and Pharmacokinetics Study of LY3451838 in Healthy Subjects

Table 14.1.2 Demographics and Baseline Characteristics (Safety)

	LY3451838							Placebo	Overall
	Cohort 1 25mgIV N=XX	Cohort 2 75mgIV N=XX	Cohort 3 250mgIV N=XX	Cohort 4 500mgIV N=XX	Cohort 5 1000mgIV N=XX	Cohort 6 1500mgIV N=XX	Cohort 7 250mgSC N=XX		
BMI (kg/m  ) N	XX	XX	XX	XX	XX	XX	XX	XX	XX
Mean	XX.X	XX.X	XX.X	XX.X	XX.X	XX.X	XX.X	XX.X	XX.X
SD	XX.X	XX.X	XX.X	XX.X	XX.X	XX.X	XX.X	XX.X	XX.X
Median	XX.X	XX.X	XX.X	XX.X	XX.X	XX.X	XX.X	XX.X	XX.X
Minimum	XX	XX	XX	XX	XX	XX	XX	XX	XX
Maximum	XX	XX	XX	XX	XX	XX	XX	XX	XX

Program: 14.1.2.xxxx.sas

Eli Lilly and Company - PROTOCOL: J1H-MC-LAJA  
 A Safety, Tolerability, and Pharmacokinetics Study of LY3451838 in Healthy Subjects

Table 14.3.1.1 ¶ Number of Subjects with Treatment-Emergent Adverse Events (Safety)

		LY3451838							Placebo	
		Cohort 1 25mgIV N=XX	Cohort 2 75mgIV N=XX	Cohort 3 250mgIV N=XX	Cohort 4 500mgIV N=XX	Cohort 5 1000mgIV N=XX	Cohort 6 1500mgIV N=XX	Cohort 7 250mgSC N=XX	Total LY N=XX	Placebo N=XX
With At Least One Adverse Event	N	xx	xx	xx	xx	xx	xx	xx	xx	
	Yes	x(xx.x%)	x(xx.x%)	x(xx.x%)	x(xx.x%)	x(xx.x%)	x(xx.x%)	x(xx.x%)	x(xx.x%)	
	No	x(xx.x%)	x(xx.x%)	x(xx.x%)	x(xx.x%)	x(xx.x%)	x(xx.x%)	x(xx.x%)	x(xx.x%)	
With At Least One Mild or Moderate Adverse Event	N	xx	xx	xx	xx	xx	xx	xx	xx	
	Yes	x(xx.x%)	x(xx.x%)	x(xx.x%)	x(xx.x%)	x(xx.x%)	x(xx.x%)	x(xx.x%)	x(xx.x%)	
	No	x(xx.x%)	x(xx.x%)	x(xx.x%)	x(xx.x%)	x(xx.x%)	x(xx.x%)	x(xx.x%)	x(xx.x%)	
With At Least One Severe Adverse Event	N	xx	xx	xx	xx	xx	xx	xx	xx	
	Yes	x(xx.x%)	x(xx.x%)	x(xx.x%)	x(xx.x%)	x(xx.x%)	x(xx.x%)	x(xx.x%)	x(xx.x%)	
	No	x(xx.x%)	x(xx.x%)	x(xx.x%)	x(xx.x%)	x(xx.x%)	x(xx.x%)	x(xx.x%)	x(xx.x%)	
With At Least One Serious Adverse Event	N	xx	xx	xx	xx	xx	xx	xx	xx	
	Yes	x(xx.x%)	x(xx.x%)	x(xx.x%)	x(xx.x%)	x(xx.x%)	x(xx.x%)	x(xx.x%)	x(xx.x%)	
	No	x(xx.x%)	x(xx.x%)	x(xx.x%)	x(xx.x%)	x(xx.x%)	x(xx.x%)	x(xx.x%)	x(xx.x%)	
With At Least One Not Related Adverse Event	N	xx	xx	xx	xx	xx	xx	xx	xx	
	Yes	x(xx.x%)	x(xx.x%)	x(xx.x%)	x(xx.x%)	x(xx.x%)	x(xx.x%)	x(xx.x%)	x(xx.x%)	
	No	x(xx.x%)	x(xx.x%)	x(xx.x%)	x(xx.x%)	x(xx.x%)	x(xx.x%)	x(xx.x%)	x(xx.x%)	
With At Least One Related Adverse Event	N	xx	xx	xx	xx	xx	xx	xx	xx	
	Yes	x(xx.x%)	x(xx.x%)	x(xx.x%)	x(xx.x%)	x(xx.x%)	x(xx.x%)	x(xx.x%)	x(xx.x%)	
	No	x(xx.x%)	x(xx.x%)	x(xx.x%)	x(xx.x%)	x(xx.x%)	x(xx.x%)	x(xx.x%)	x(xx.x%)	

Program: 14.3.1.1.xxxx.sas

Eli Lilly and Company - PROTOCOL: J1H-MC-LAJA  
 A Safety, Tolerability, and Pharmacokinetics Study of LY3451838 in Healthy Subjects

Table 14.3.1.2 T Number of Treatment-Emergent Adverse Events (Safety)

	LY3451838							Total LY	Placebo
	Cohort 1 25mgIV N=XX	Cohort 2 75mgIV N=XX	Cohort 3 250mgIV N=XX	Cohort 4 500mgIV N=XX	Cohort 5 1000mgIV N=XX	Cohort 6 1500mgIV N=XX	Cohort 7 250mgSC N=XX		
	xx	xx	xx	xx	xx	xx	xx		
Adverse Event	xx	xx	xx	xx	xx	xx	xx	xx	xx
Mild or Moderate Adverse Events	xx	xx	xx	xx	xx	xx	xx	xx	xx
Severe Adverse Events	xx	xx	xx	xx	xx	xx	xx	xx	xx
Serious Adverse Events	xx	xx	xx	xx	xx	xx	xx	xx	xx
Adverse Events Not Related To Study Drug	xx	xx	xx	xx	xx	xx	xx	xx	xx
Adverse Events Related To Study Drug	xx	xx	xx	xx	xx	xx	xx	xx	xx

Eli Lilly and Company - PROTOCOL: J1H-MC-LAJA  
 A Safety, Tolerability, and Pharmacokinetics Study of LY3451838 in Healthy Subjects

Table 14.3.1.3 T Number of Subjects with TEAE by MedDRA System Organ Class /Preferred Term (Safety)

System Organ Class/ Preferred Term	LY3451838							Total LY	Placebo
	Cohort1	Cohort2	Cohort3	Cohort4	Cohort5	Cohort6	Cohort7		
	25mgIV N=XX	75mgIV N=XX	250mgIV N=XX	500mgIV N=XX	1000mgIV N=XX	1500mgIV N=XX	250mgSC N=XX		
System Organ Class #1									
Preferred Term #1.1	xx(xx.x%)	xx(xx.x%)	xx(xx.x%)	xx(xx.x%)	xx(xx.x%)	xx(xx.x%)	xx(xx.x%)	xx(xx.x%)	xx(xx.x%)
Preferred Term #1.2	xx(xx.x%)	xx(xx.x%)	xx(xx.x%)	xx(xx.x%)	xx(xx.x%)	xx(xx.x%)	xx(xx.x%)	xx(xx.x%)	xx(xx.x%)
Preferred Term #1.3	xx(xx.x%)	xx(xx.x%)	xx(xx.x%)	xx(xx.x%)	xx(xx.x%)	xx(xx.x%)	xx(xx.x%)	xx(xx.x%)	xx(xx.x%)
System Organ Class #2									
Preferred Term #2.1	xx(xx.x%)	xx(xx.x%)	xx(xx.x%)	xx(xx.x%)	xx(xx.x%)	xx(xx.x%)	xx(xx.x%)	xx(xx.x%)	xx(xx.x%)
Preferred Term #2.2	xx(xx.x%)	xx(xx.x%)	xx(xx.x%)	xx(xx.x%)	xx(xx.x%)	xx(xx.x%)	xx(xx.x%)	xx(xx.x%)	xx(xx.x%)
Preferred Term #2.3	xx(xx.x%)	xx(xx.x%)	xx(xx.x%)	xx(xx.x%)	xx(xx.x%)	xx(xx.x%)	xx(xx.x%)	xx(xx.x%)	xx(xx.x%)

Multiple events with the same preferred term in a system organ class for a subject are only counted once in the statistics of that preferred term.

Program: 14.3.1.3.xxxx.sas

Eli Lilly and Company - PROTOCOL: J1H-MC-LAJA  
 A Safety, Tolerability, and Pharmacokinetics Study of LY3451838 in Healthy Subjects

Table 14.3.1.4 Number of Subjects with TEAE by MedDRA System Organ Class /Preferred Term and Severity (Safety)

Treatment: LY3451838 (cohort 1 - 25 mg IV)

System Organ Class / Preferred Term	Severity N (%)			
	Mild	Moderate	Severe	Very Severe
System Organ Class #1				
Preferred Term #1.1	xx (xx.x%)	xx (xx.x%)	xx (xx.x%)	xx (xx.x%)
Preferred Term #1.2	xx (xx.x%)	xx (xx.x%)	xx (xx.x%)	xx (xx.x%)
Preferred Term #1.3	xx (xx.x%)	xx (xx.x%)	xx (xx.x%)	xx (xx.x%)
etc.				
System Organ Class #2				
Preferred Term #2.1	xx (xx.x%)	xx (xx.x%)	xx (xx.x%)	xx (xx.x%)
Preferred Term #2.2	xx (xx.x%)	xx (xx.x%)	xx (xx.x%)	xx (xx.x%)
Preferred Term #2.3	xx (xx.x%)	xx (xx.x%)	xx (xx.x%)	xx (xx.x%)
etc.				

For multiple events with the same preferred term in a system organ class for a subject, the most severe one is counted. The percentage represents the incidence of an event by the preferred term as a percentage of the total number of subjects in the treatment group.

Program: 14.3.1.4.xxxx.sas

Eli Lilly and Company - PROTOCOL: J1H-MC-LAJA  
A Safety, Tolerability, and Pharmacokinetics Study of LY3451838 in Healthy Subjects

Table 14.3.1.5 T Number of Subjects with TEAE by MedDRA System Organ Class /Preferred Term and Severity (Safety)

Treatment: LY3451838 (cohort 1- 25 mg IV)

Number Of Subjects: xx \_\_\_\_\_ Relationship to Study Drug N (%) \_\_\_\_\_

System Organ Class / Preferred Term

Unrelated

Related

---

System Organ Class #1

Preferred Term #1.1  
Preferred Term #1.2  
Preferred Term #1.3  
etc.

xx (xx.x%)

xx (xx.x%)

xx (xx.x%)

xx (xx.x%)

xx (xx.x%)

xx (xx.x%)

System Organ Class #2

Preferred Term #2.1  
Preferred Term #2.2  
Preferred Term #2.3  
etc.

xx (xx.x%)

xx (xx.x%)

xx (xx.x%)

xx (xx.x%)

xx (xx.x%)

xx (xx.x%)

For multiple events with the same preferred term in a system organ class for a subject, the one with the most closely related to the study drug is counted. The percentage represents the incidence of an event by the preferred term as a percentage of the total number of subjects in the study group.

Program: 14.3.1.5.xxxx.sas

Eli Lilly and Company - PROTOCOL: J1H-MC-LAJA  
 A Safety, Tolerability, and Pharmacokinetics Study of LY3451838 in Healthy Subjects

Table 14.3.4.4 Laboratory Test Results - C3, C4, CRP and ESR (Safety)

Number of Subjects with Significant Decrease in C3	LY3451838							Total LY	Placebo
	Cohort 1 25mgIV N=XX	Cohort 2 75mgIV N=XX	Cohort 3 250mgIV N=XX	Cohort 4 500mgIV N=XX	Cohort 5 1000mgIV N=XX	Cohort 6 1500mgIV N=XX	Cohort 7 250mgSC N=XX		
Post-baseline Visit #1	N	xx	xx	xx	xx	xx	xx	xx	xx
	YES	x(xx.x%)	x(xx.x%)	x(xx.x%)	x(xx.x%)	x(xx.x%)	x(xx.x%)	x(xx.x%)	x(xx.x%)
	NO	x(xx.x%)	x(xx.x%)	x(xx.x%)	x(xx.x%)	x(xx.x%)	x(xx.x%)	x(xx.x%)	x(xx.x%)
Post-baseline Visit #2	N	xx	xx	xx	xx	xx	xx	xx	xx
	YES	x(xx.x%)	x(xx.x%)	x(xx.x%)	x(xx.x%)	x(xx.x%)	x(xx.x%)	x(xx.x%)	x(xx.x%)
	NO	x(xx.x%)	x(xx.x%)	x(xx.x%)	x(xx.x%)	x(xx.x%)	x(xx.x%)	x(xx.x%)	x(xx.x%)

...

The baseline is the measurement at Visit 3 prior to dosing, or Visit 2 whichever is the last available one.  
 Program: 14.3.4.4.xxx.sas

Eli Lilly and Company - PROTOCOL: J1H-MC-LAJA  
 A Safety, Tolerability, and Pharmacokinetics Study of LY3451838 in Healthy Subjects

Table 14.3.4.5  $\bar{T}$  Immunogenicity (Safety)

	LY3451838							Total LY	Placebo
	Cohort 1 25mgIV N=XX	Cohort 2 75mgIV N=XX	Cohort 3 250mgIV N=XX	Cohort 4 500mgIV N=XX	Cohort 5 1000mgIV N=XX	Cohort 6 1500mgIV N=XX	Cohort 7 250mgSC N=XX		
Subject Evaluable for TEADA*	x (xx.x%)	x (xx.x%)	x (xx.x%)	x (xx.x%)	x (xx.x%)	x (xx.x%)	x (xx.x%)	x (xx.x%)	x (xx.x%)
Subject with ADA Detected at Baseline	x (xx.x%)	x (xx.x%)	x (xx.x%)	x (xx.x%)	x (xx.x%)	x (xx.x%)	x (xx.x%)	x (xx.x%)	x (xx.x%)
Subject with TEADA+ at Post-baseline**	x (xx.x%)	x (xx.x%)	x (xx.x%)	x (xx.x%)	x (xx.x%)	x (xx.x%)	x (xx.x%)	x (xx.x%)	x (xx.x%)
Treatment-Induced	x (xx.x%)	x (xx.x%)	x (xx.x%)	x (xx.x%)	x (xx.x%)	x (xx.x%)	x (xx.x%)	x (xx.x%)	x (xx.x%)
Treatment-Boosted	x (xx.x%)	x (xx.x%)	x (xx.x%)	x (xx.x%)	x (xx.x%)	x (xx.x%)	x (xx.x%)	x (xx.x%)	x (xx.x%)

\* Subjects evaluable for TEADA if there is at least one baseline assessment and at least post-baseline assessment of ADA.

\*\* Treatment-emergent ADAs are defined as those with a titer 2-fold (1dilution) greater than the minimum required dilution if no ADAs were detected at baseline (treatment-included ADA) or those with a 4-fold (2 dilutions) increase in titer compared to baseline if ADAs were detected at baseline (treatment-boosted ADA).

Program: 14.3.4.5.xxx.sas

Eli Lilly and Company - PROTOCOL: J1H-MC-LAJA  
 A Safety, Tolerability, and Pharmacokinetics Study of LY3451838 in Healthy Subjects

Table 14.3.4.6  $\bar{T}$  PACAP Concentration (Safety)

3451838P		LY3451838							Total LY	Placebo
		Cohort 1 25mgIV N=XX	Cohort 2 75mgIV N=XX	Cohort 3 250mgIV N=XX	Cohort 4 500mgIV N=XX	Cohort 5 1000mgIV N=XX	Cohort 6 1500mgIV N=XX	Cohort 7 250mgSC N=XX		
Baseline		XX	XX	XX	XX	XX	XX	XX	XX	XX
	Mean	XX.X	XX.X	XX.X	XX.X	XX.X	XX.X	XX.X	XX.X	XX.X
	SD	XX.X	XX.X	XX.X	XX.X	XX.X	XX.X	XX.X	XX.X	XX.X
	Median	XX.X	XX.X	XX.X	XX.X	XX.X	XX.X	XX.X	XX.X	XX.X
	Minimum	XX	XX	XX	XX	XX	XX	XX	XX	XX
	Maximum	XX	XX	XX	XX	XX	XX	XX	XX	XX
Post-baseline #1		XX	XX	XX	XX	XX	XX	XX	XX	XX
	Mean	XX.X	XX.X	XX.X	XX.X	XX.X	XX.X	XX.X	XX.X	XX.X
	SD	XX.X	XX.X	XX.X	XX.X	XX.X	XX.X	XX.X	XX.X	XX.X
	Median	XX.X	XX.X	XX.X	XX.X	XX.X	XX.X	XX.X	XX.X	XX.X
	Minimum	XX	XX	XX	XX	XX	XX	XX	XX	XX
	Maximum	XX	XX	XX	XX	XX	XX	XX	XX	XX
Change from Baseline to Post-baseline #1		XX	XX	XX	XX	XX	XX	XX	XX	XX
	Mean	XX.X	XX.X	XX.X	XX.X	XX.X	XX.X	XX.X	XX.X	XX.X
	SD	XX.X	XX.X	XX.X	XX.X	XX.X	XX.X	XX.X	XX.X	XX.X
	Median	XX.X	XX.X	XX.X	XX.X	XX.X	XX.X	XX.X	XX.X	XX.X
	Minimum	XX	XX	XX	XX	XX	XX	XX	XX	XX
	Maximum	XX	XX	XX	XX	XX	XX	XX	XX	XX

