| Evaluate the pharmacokinetics of LY3451838 in healthy subjects following a single dose of LY3451838. | 
 • AUC • C_{max} |

Abbreviations: AUC = area under the concentration-time curve; C_{max} = maximum drug concentration

Summary of Study Design:

Study J1H-MC-LAJA is a first-in-human, investigator- and subject-blind, placebo-controlled, randomized, 2-part study in healthy subjects to evaluate the safety, tolerability, and pharmacokinetics of LY3451838. In Part A, the single ascending doses of LY3451838 will be administered IV in up to 6 cohorts of 8 subjects each. In Part B, a single dose of LY3451838 will be administered SC in up to 2 cohorts of 8 subjects each.

Safety / tolerability, pharmacokinetic, immunogenicity, and exploratory pharmacodynamic assessments will be performed at prescribed time points during the stay at the clinical research unit (CRU) and at subsequent study visits.

All available safety and PK data will be reviewed before each dose escalation. The proposed doses may be adjusted after review of available data from previous dose levels after consultation with a Safety Review Panel (SRP) that is independent of the team.

Treatment Arms and Planned Duration for an Individual Subject:

In both parts, within each cohort, subjects will be randomly assigned to receive LY3451838 or placebo in a 6:2 ratio.

Part A: LY3451838 will be administered IV, at single ascending dose levels, starting at 25 mg and escalated up to 1500 mg.

Part B: LY3451838 will be administered SC as a single dose, which is planned as a 250 mg dose or a dose that matches that of Cohort 3 in Part A. Up to 2 cohorts in Part B may be enrolled to explore various features of SC dosing at the same dose level.

In both parts, subjects will be followed for approximately 20 weeks following administration of the study drug.

Number of Subjects:

Up to 80 healthy subjects may be enrolled so that approximately 6 subjects in each LY3451838 dosing group complete the 20-week study. Any subject who was withdrawn before completion of all study activities may be replaced at the discretion of the Sponsor.

Statistical Analysis:

Safety: The primary safety endpoints are the numbers and types of treatment-emergent serious adverse events and adverse events. Summary statistics for each cohort will be provided by dose level and for all placebo subjects combined.

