7.4.1.1 Stopping Rules

If any of the following occur, dosing at the current level and further dose escalation will be discontinued:

1. A single subject experiences an SAE that is related to LY3451838

- a. If an SAE occurs during the infusion of study drug, irrespective of causality, the study drug is discontinued immediately in that subject. No redosing or completion of dosing is considered for that subject regardless of causality. If the infusion SAE is considered related to LY3451838, then the remaining subjects in that cohort are not dosed.
2. Two or more cumulative subjects develop clinically significant acute infusion AEs considered related to LY3451838 during or within 6 hours of completing the infusion that do not resolve with a reduced infusion rate and/or supportive care.
3. Two or more cumulative subjects develop clinically significant hypersensitivity AEs considered related to LY3451838
4. Two or more cumulative subjects experience similar clinically significant events (CSEs) considered related to LY3451838. A CSE will be defined as a moderate-to-severe AE, abnormal clinical sign, or clinical laboratory finding that may pose a risk to the well-being of the subject.
5. 50% or more subjects at a dose level experience moderate or severe AEs that impair normal activities, but do not meet the CSE criteria, and are considered related to LY3451838.

Two or more subjects experience severe adverse reactions, irrespective of their nature.

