# **9.      ANALYSIS OF SAFETY ENDPOINTS**

## 9.1 Adverse Events

The adverse events will be coded by the Medical Dictionary for Drug Regulatory Activities (MedDRA) version 22.0. The treatment-emergent adverse event (TEAE) is defined as any AE emerging or worsening after start of investigational medicinal product (IMP) administration (including placebo). Summary tables will include number of subjects reporting TEAEs and as percentage of number of subjects for the overall subjects. The number of serious TEAEs will be summarized in the appropriate summary table. Summary tables will also be presented for the frequency of adverse events by the MedDRA system organ class and preferred term. Multiple events in the same system organ class for a subject are only counted once in the statistics of that system organ class. The SOC will be presented alphabetically and preferred term within SOC will be presented in descending order of overall frequency. Summary tables will also be provided for the frequency of adverse events by MedDRA system organ class and preferred term and severity of adverse events, and relationship of adverse events to study drug. In these summaries, the most extreme outcome (highest severity and closest relationship to study drug) will be used for those subjects who experience the same adverse event (per preferred term) on more than one occasion.

The number and percentage of patients with Serious TEAE by SOC and preferred term will be summarized. An individual listing of serious TEAE will also be provided.

The summary tables will be performed by each cohort in LY3451838, overall LY3451838 and all placebo subjects combined.

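### The planned adverse-event tables do not give, and cannot yield, the number of subjects per dose with at least one moderate-or-worse TEAE

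*SAP*

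**What the plan says.** The Protocol Synopsis defines the endpoint: "The primary safety endpoints are the numbers and types of treatment-emergent serious adverse events and adverse events". Tolerability by dose is part of the primary objective.

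In SAP Section 13, the shell for Table 14.3.1.1 counts subjects. Its severity rows are "With At Least One Mild or Moderate Adverse Event" and "With At Least One Severe Adverse Event". The shell for Table 14.3.1.2 counts events and again has one pooled row, "Mild or Moderate Adverse Events", beside a severe row.

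One planned table separates mild from moderate. SAP Section 12.1 lists it as Table 14.3.1.5, "Number of Subjects with TEAE by MedDRA System Organ Class / Preferred Term and Severity" (its shell is numbered 14.3.1.4). It is laid out one treatment group at a time, with columns for mild, moderate, severe and very severe. Its footnote reads "For multiple events with the same preferred term in a system organ class for a subject, the most severe one is counted". SAP Section 9.1 gives the same rule in the text: the worst grade "will be used for those subjects who experience the same adverse event (per preferred term) on more than one occasion". The shell has no row for any TEAE.

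In Protocol Section 7.4.1.1, rule 5 refers to the case where "50% or more subjects at a dose level experience moderate or severe AEs that impair normal activities". Rule 4 works through a definition of a clinically significant event that also starts at moderate severity.

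**The concern.** In a descriptive first-in-human study with about 6 active subjects per dose, simple subject counts by dose are the main evidence on tolerability. A natural question is how many subjects at each dose had something worse than a mild event. Stopping rules 4 and 5 draw their severity line in the same place, between mild and moderate. The headline tables draw it between moderate and severe. If events move from mild to moderate as the dose rises, with no change in who is affected, both severity rows of both headline tables stay the same.

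The preferred-term table does not supply the missing number. A subject with moderate events under three terms appears in three rows, so the rows cannot be added to give subjects.

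A smaller inconsistency is that the severity shell has a very severe column, while neither headline table has a matching severity row.

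**Working it through.** The documents give no figure for this count, and Protocol Section 10.1 says the study is not powered on a hypothesis test. There is therefore no stated number to reproduce. The check is whether the count can be recovered from the planned tables.

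**Inputs.** n = 6 active subjects per cohort (6:2 allocation, Protocol Section 7.2); the rows of Tables 14.3.1.1 and 14.3.1.2; and the preferred-term severity table, which takes the worst grade per term per subject.

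**Step 1: what the preferred-term table allows.** Let m_j be the number of subjects whose worst grade under term j is moderate or worse, and N the number of subjects with any moderate-or-worse TEAE. The terms may affect the same or different subjects, so

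max(m_j) ≤ N ≤ min(n, sum of m_j).

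Enumerating all arrangements with n = 6 gives:

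| m_j by term | possible N | as % of 6 |
|---|---|---|
| 1 | 1 | 16.7 |
| 1, 1 | 1 to 2 | 16.7 to 33.3 |
| 1, 1, 1 | 1 to 3 | 16.7 to 50.0 |
| 2, 1 | 2 to 3 | 33.3 to 50.0 |
| 2, 2 | 2 to 4 | 33.3 to 66.7 |
| 2, 2, 1 | 2 to 5 | 33.3 to 83.3 |

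N is exact only in simple cases, such as a single affected term or no moderate-or-worse event.

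**Step 2: whether the headline tables settle it.** Take three preferred terms P, Q and R in different system organ classes, no serious events, and all events with the same relatedness.

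| Subject | Data set A | Data set B |
|---|---|---|
| 1 | P, Q, R all moderate | P moderate, Q mild |
| 2 | P mild | Q moderate, R mild |
| 3 | Q mild | R moderate |
| 4 | R mild | P mild |
| 5, 6 | none | none |

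The planned tables then show:

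| Planned output | A | B |
|---|---|---|
| Subjects with any AE | 4 | 4 |
| Subjects with mild or moderate AE | 4 | 4 |
| Subjects with severe AE | 0 | 0 |
| Mild or moderate events | 6 | 6 |
| Severe events | 0 | 0 |
| Each of P, Q, R: mild / moderate subjects | 1 / 1 | 1 / 1 |
| **Subjects with moderate or worse (not planned)** | **1/6 = 16.7%** | **3/6 = 50.0%** |

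Every planned cell is the same, yet the missing count differs threefold.

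**Step 3: what the added rows would show.** By worst severity per subject, A gives mild 3, moderate 1, severe 0; B gives mild 1, moderate 3, severe 0. Each set adds to the 4 subjects with any AE, so the rows check themselves. Splitting the event counts alone would not be enough, because both data sets have 3 mild and 3 moderate events.

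**The case against.** The strongest reply is that the endpoint is the number and type of TEAEs, which the plan reports, and that how severity is grouped in an overview table is a matter of presentation. SAP Section 13 also says the shells show general layout and may not cover everything. This limits the weight of the point but does not remove it. Nothing in SAP Section 9.1 adds a subject-level count by severity, so the shells are the only statement of what will be produced.

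Three stronger readings are tempting, and the documents do not support them.

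- A reader might infer that the report could not show a move from mild to moderate with dose. It could. The preferred-term table shows moderate counts in each cohort, Protocol Section 10.3.1 promises a listing of AEs, and SAP Section 12.2 plans Listing 11 or equivalent raw listings. With 6 active subjects per cohort a hand count is feasible. What is missing is the planned subject-level total across terms.
- A reader might infer that the stopping rules cannot be applied. They are judged during the study from ongoing review (Protocol Sections 7.4.1 and 10.3.5), not from these final tables. Rules 4 and 5 also need relatedness. Rule 4 needs similar events. Rule 5 needs an effect on normal activities and excludes clinically significant events. The last rule uses severe reactions only. The match is on the severity cut-point alone. The 3/6 in data set B equals the 50% share in rule 5 but does not show that rule 5 is met. If all 8 cohort subjects formed the denominator, it would be 3/8 = 37.5%.
- A reader might infer that a very severe event would disappear from the headline tables. It would still count in their all-AE and relatedness rows. It would only lack a severity row of its own, unless severe is meant to include it, which the SAP does not say. Nothing in the text shows that this grade is collected.

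**Conclusion.** The point holds as a reporting gap. No planned summary table gives the number of subjects per dose with at least one moderate-or-worse TEAE, and the planned tables together only bound it. In a cohort of 6 the range can run from 1/6 to 3/6 on identical output. With per-term counts of 2, 2 and 1, the preferred-term table alone allows 2/6 to 5/6. The data sets are illustrations, not forecasts, and assume terms in different system organ classes. If few moderate events occur, or all fall under one term, the gap closes by itself.

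The gap touches the primary tolerability objective, but no safety decision, dose step or collected data item depends on it. It is worth correcting because the present grouping loses information that costs almost nothing to keep.

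**What to change.** - **Table 14.3.1.1:** replace the pooled row with mild, moderate and severe rows by each subject's worst severity across all TEAEs. Add two rows: subjects with at least one moderate-or-worse TEAE, and subjects with at least one related moderate-or-worse TEAE. For the second, the same event must meet both conditions; no planned table crosses severity with relatedness.
- **Table 14.3.1.2:** count mild, moderate and severe events separately.
- **All AE tables:** use one severity scale. Either drop the very severe column or carry that grade through every table.
- **SAP Section 9.1:** add a sentence defining worst severity per subject across all TEAEs, beside the existing rule per preferred term.

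The cost is a shell edit and a few lines of code on severity and relatedness, both of which the SAP already tabulates. Nothing in dosing, procedures or data collection changes. SAP Section 6 refers to a data lock. If the tables have already been run, the addition can be recorded as SAP Section 2 provides, in a change request or note to file and in the CSR.
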